**6.2.4.8.2**

[REDACTED]

[REDACTED]

**6.2.4.9.**

[REDACTED]

[REDACTED]

**6.2.4.9.1**

[REDACTED]

[REDACTED]

**6.2.4.9.2**

[REDACTED]

[REDACTED]

**6.2.5. Subgroup Analyses**

No subgroup analysis is planned for this clinical study as the study sample size is too small. Thus, any subgroup of this would have small sample size to be relevant or even uninterpretable.

## 6.3. Safety Analyses

Safety analyses will be performed on the Safety Analysis Set.

Safety tables will be presented by treatment group.

Safety parameters will be analyzed descriptively (see [Section 4.5.2](#) and [Section 4.5.3](#)). No formal testing will be performed to compare the treatment groups.

### 6.3.1. Adverse Events

All adverse events (AEs) and changes in attributes (worsening and improvement) of AEs are reported in the database. An identification number serves to link the records considered by the investigator as describing the evolution of one and the same event.

#### 6.3.1.1. Definition of Treatment-Emergent Adverse Events

The analysis of AEs will be based on treatment-emergent events (TEAE).

TEAEs are defined as

- Any AE with an onset date on or after the IP start date and no later than 30 days after last dose of IP, or any worsening of any AE on or after the IP start date.
- Improvement or no change of any ongoing AEs on or after the IP start date are not considered treatment-emergent. If an AE is ongoing at the time of first IP intake, if there is no change or an improvement in its toxicity grade or its seriousness status (reported in the 'Change in Adverse event details Entry' CRF page), this AE will not be considered as treatment-emergent.

#### 6.3.1.2. Coding of Reported Terms

All AE terms will be coded in the database using the latest version of MedDRA coding dictionary. AEs will be graded using the latest version of the National Cancer Institute Common Terminology Criteria for Adverse Events (NCI CTCAE).

All tables will show the AE preferred terms grouped into system organ class. Subject listings will also show the reported terms (verbatim). Any other coding levels will only be shown in a listing summarizing coding unless explicitly mentioned otherwise.

#### 6.3.1.3. Allocation of Adverse Events to Analysis Periods

All AEs will be placed into analysis periods considering their start date, aiming to report the incidence of these events only in the analysis period during which they started.

The general rule for allocation of AEs to analysis periods follows:

Analysis period start date  $\leq$  AE start date  $\leq$  analysis period end date

If the start date of an AE is missing or incomplete to a level preventing a clear allocation of the AE to one single analysis period and no flag indicating timing relative to study medication is available, a worst-case consideration (see below) will be done aiming to allocate the AE to one single analysis period, if possible. When a worst-case consideration is needed, the end date of the AE, if and as available, should also be considered; if such AEs clearly end on a given point, this will exclude the possibility to allocate the AE to an analysis period after that point.

- An AE which according to the available information of its start date could belong to the screening as well as to the treatment analysis period will only be placed in the treatment period.
- An AE with a missing start date will be allocated to the treatment period unless the “Prior to First GLPG3970/Placebo Treatment” = “Yes”.

#### **6.3.1.4. Treatment Relatedness**

Following the guideline ICH-E3 Structure and Content of Clinical Study Reports (Step 4 Version), the originally reported relatedness to IP of an AE will be dichotomized as follows:

- *Not IP related*: all non-missing weaker levels of relatedness than ‘possibly drug related’.
- *IP related*: ‘possibly drug related’ and all stronger levels of relatedness (this class also includes any missing drug relatedness, as a worst-case consideration).

Only this dichotomized relatedness will be used in tables and can apply to different IPs when relatedness has been collected separately per IP; relatedness as originally reported will only be listed.

#### **6.3.1.5. Worst-Case Selections**

When cross-tabulating AE preferred terms versus an AE attribute (like intensity), only the worst-case within each same preferred term, same subject and same analysis period will be considered, i.e. when the same subject has more than once the same AE preferred term reported in the same treatment group, the subject will be counted only once and will be shown under the worst outcome (like the worst intensity for that AE in the concerned treatment period).

The severity grade of events for which the investigator did not record severity will be categorized as “missing” for tabular summaries and data listings. The missing category will be presented last in summary presentation.

#### **6.3.1.6. Calculation of Relative Days and Duration**

For each newly reported event, and reported worsening or improvement of an existing event, the start day in the study (the day of the AE start date relative to the date of first IP administration), the start day in the analysis period, and the duration (in days) will be calculated. In addition, the relative day and duration will be derived for the entire event; that is, the full evolution of the event, including the initial reporting and all subsequent worsening and/or improvement.

Relative days and durations will only be listed.

See [Section 4.3.1](#) for the calculation of relative days.

#### **6.3.1.7. Events of Special Interest**

Not applicable.

#### **6.3.1.8. Presentation of Results**

The analysis will focus on AEs reported during the treatment period. AEs reported during the screening period will only be listed.

All AEs tables will show the number of subjects with TEAEs.

AEs which are not treatment-emergent will only be listed.

A summary table will be provided, showing the number (percent) of subjects with at least one:

- TEAE,
- IP-related TEAE,
- Serious TEAE,
- TEAE leading to death,
- TEAEs by worst intensity (CTCAE Toxicity Grade),
- TEAE leading to IP interruption,
- TEAE leading to IP discontinuation.

The AE terms will be presented sorted in descending order of frequency, prioritizing the GLPG3970 treatment group and then for placebo, first by system organ class, then by preferred term, and then alphabetically.

Frequency tabulations, by system organ class and preferred term, of the number (percent) of subjects with a TEAE will be presented. Similar tables will be provided by worst intensity, and for IP-related TEAEs, grade 3-4-5 TEAEs, serious TEAEs and TEAEs leading to IP discontinuation of IP.

All AE data will also be listed, including separate lists for SAEs, AEs leading to death, and AEs leading to IP discontinuation. Listings will clearly indicate AEs to be treatment-emergent or not.

In addition, AEs related to SARS-CoV-2 will be listed separately.

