## 1. INTRODUCTION

This statistical analysis plan (SAP) describes the final statistical analyses of study GLPG3970-CL-207. The results of the analysis will be described in the clinical study report (CSR).

Technical details on derivations and mock tables, listings and figures (TLFs) will be presented in a separate document.

The statistical analysis will process and present the results following the International Council for Harmonization (ICH) standards, particularly the ICH-E3, ICH-E6, ICH-E9, ICH-R9 (R1) and ICH-E14 guidelines.

On 26 November 2021, the Safety Monitoring Committee recommended to immediately terminate Study GLPG3970-CL-207 due to a safety signal of liver toxicity. Therefore, the GLPG3970-CL-207 study was prematurely stopped. In view of this, only the primary endpoint and safety analyses will be performed. Results will be presented in an abbreviated CSR. Any provisions no longer applicable following premature study termination are highlighted in grey.

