### 2.2.1. Primary Endpoints

- Change from baseline in European League against Rheumatism (EULAR) Sjögren's Syndrome Disease Activity Index (ESSDAI) score at Week 12.
- Number, incidence, and severity of treatment-emergent adverse events (TEAEs).

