### 2.2.3. Other Endpoints

## 2.3. Study Design

This is a Phase 2a, randomized, double-blind, placebo-controlled, parallel-group, multicenter study to evaluate the efficacy, safety, tolerability, PK, [REDACTED] of orally administered GLPG3970 for 12 weeks in adult subjects with active pSS.

One dose level of GLPG3970 will be evaluated in 30 subjects who will be randomized 2:1 to receive GLPG3970 (400 mg [2 x 200 mg] qd) or matching placebo, respectively.

The study will consist of 3 study periods:

[figure not shown]
- Screening period: up to 4 weeks with 1 study visit. During the Screening visit, subjects will be selected based on the eligibility criteria. Subjects already on treatment will remain on a stable standard of care (SoC) treatment during the study.
- Treatment period: 12 weeks with up to 5 study visits (Days 1, 8, 29, 57, and 85). At any time during the course of the study, phone calls or unscheduled visits can be added if deemed necessary by the investigator. Subjects will receive GLPG3970 or placebo qd.
- Follow-up (FU) period: 4 weeks with 1 study visit. Subjects remain on stable SoC treatment, if applicable.

The subjects will be in the study for a duration of 20 weeks: up to 4 weeks of screening, 12 weeks of treatment, and 4 weeks of FU.

Refer to the Schedule of Assessments ([Section 2.5](#)) for further details.

A schematic diagram of clinical study design and periods is provided in [Figure 1](#).

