### 3. STUDY ESTIMANDS

Estimand for the primary endpoints:

Attribute	Details
Treatments	GLPG3970 (400 mg qd) vs. Placebo
Population	

Population target defined through the inclusion/exclusion criteria (see CSP section 6).

Analysis Set: Full Analysis Set (FAS), defined as all randomized subjects who have received at least one dose of IP.

Endpoint	Change from baseline in ESSDAI score at Week 12.
Population-level summary	Difference (GLPG3970-Placebo) in least square mean (LSM). For further details see study SAP section 6.2.2.2 .
Intercurrent events and strategies to handle those	

Early treatment discontinuation (for any reason) is handled using the hypothetical strategy

Other intercurrent events (e.g. major protocol violations, intake of prohibited medication, lack of compliance) are handled using the

	treatment policy strategy (i.e. they are ignored)
--	---

Estimand for the safety endpoint

Attribute	Details
Treatments	GLPG3970 (400 mg qd) vs. Placebo
Population	

Population target defined through the inclusion/exclusion criteria (see CSP).

Analysis Set: Safety Analysis Set, defined as all randomized subjects who have received at least one dose of IP.

Endpoint	Presence of TEAE
Population-level summary	Percentage of subjects with TEAEs.
Intercurrent events and strategies to handle these	Intercurrent event: 

Early treatment discontinuation (for any reason): handled using the while-on-treatment strategy. All collected data up to (and including) the last contact visit is regarded as possibly influenced by the drug exposure and thus will be used in the analysis.

Intercurrent event: major protocol deviations, intake of prohibited/rescue medication, lack of compliance): handled using the treatment policy strategy. All collected data will be used in the analysis.

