#### **4.5.3. Calculation of Percentages**

Frequencies and percentages will be generated for categorical parameters.

For event-type data (e.g. adverse events), the denominator will be all subjects in the analysis set and analysis period. For other data (e.g. worst-case analysis of assessments), the denominator will be all subjects with (post-baseline) data for the parameter, in the analysis set and analysis window/period.

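### TEAEs are summarised only as crude subject percentages although time at risk varies; an exposure-adjusted rate beside n (%) would be a cheap improvement

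*SAP*

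**What the plan says.** The safety estimand in SAP section 3 has as its population-level summary "Percentage of subjects with TEAEs". SAP 4.5.3 fixes the denominator: "For event-type data (e.g. adverse events), the denominator will be all subjects in the analysis set and analysis period". SAP 6.3.1.8 then applies this throughout: "All AEs tables will show the number of subjects with TEAEs". Protocol 9.3.5.2 likewise asks for numbers and percentages of subjects.

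Time at risk is tied to dosing. Under SAP 6.3.1.1 a new event counts as treatment-emergent if it starts "no later than 30 days after last dose of IP". A subject who stops early is asked only for an early discontinuation visit and a follow-up visit 28 ± 3 days after the last dose (Protocol 6.4 and 8.11). SAP section 3 adds: "Early treatment discontinuation (for any reason): handled using the while-on-treatment strategy", but in the same row it uses all data up to last contact.

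Other provisions nearby:
- Treatment duration is summarised by arm (SAP 6.1.8) but is not linked to adverse events.
- Relative days and durations of adverse events are only listed (SAP 6.3.1.6), and censoring of time-to-event data is marked not applicable (SAP 4.4.1.3).
- The SAP is dated 17 December 2021. Its introduction reports the committee's recommendation of 26 November 2021 to terminate because of a liver signal, records that "the GLPG3970-CL-207 study was prematurely stopped", and limits the analyses to the primary endpoint and safety.

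**The concern.** A crude percentage compares arms fairly when subjects in both are observed for similar times. Here a subject who stops the study drug also stops contributing to the TEAE window about a month later. If one arm has more early stops, its subjects have less time in which other events can appear, and its percentages for those events fall for a reason unrelated to the drug's safety.

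The documents name plausible routes to uneven stopping. Protocol 6.4 requires discontinuation for certain liver, ECG and infection findings, and Protocol 5.5 lists QT prolongation and serious infections among the potential risks. The study itself ended on a liver signal. Because the report is abbreviated, the adverse event tables are one of its main products, and readers will compare the two columns even without a formal test. At stake is how the system organ class and preferred term tables are read, most of all for events that tend to start late.

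**Working it through.** The plan gives no TEAE rate, expected exposure or safety precision to reproduce. Its only sizing figures (SAP 2.6) concern ESSDAI and do not bear on this point.

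**Inputs from the documents.** Treatment lasts 12 weeks = 84 days; the TEAE tail is 30 days; 20 and 10 subjects are planned.

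**Assumed inputs.** Full-window TEAE percentage p = 30-70%; share f of one arm stopping early = 10-50%; stop after 28 or 56 days; no early stops in the other arm; a constant hazard, equal in both arms, so that the true rate ratio is 1.

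**Step 1: window lengths.** Full: 84 + 30 = 114 days. Stop after 28 days: 28 + 30 = 58 days, or 51% of 114. Stop after 56 days: 56 + 30 = 86 days, or 75%.

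**Step 2: TEAEs other than the stopping event.** The daily hazard is λ = -ln(1 - p)/114. The probability of an event in a shortened window w is q = 1 - exp(-λw). The crude percentage in the arm with stops is (1 - f)p + fq.

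For p = 50%, λ = 0.6931/114 = 0.00608, and a stop after 28 days gives q = 1 - exp(-0.00608 × 58) = 29.7%. With f = 30%: 0.7 × 50 + 0.3 × 29.7 = 43.9%, against 50% in the other arm.

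**Step 3: any TEAE when every stopping event is itself a TEAE.** The percentage is (1 - f)p + f. With p = 50% and f = 30%: 35 + 30 = 65%.

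| f (p = 50%, stop after 28 days) | Other TEAEs | Gap, points | Any TEAE, stops counted | Gap, points |
|---|---|---|---|---|
| 10% | 48.0% | -2.0 | 55% | +5 |
| 20% | 45.9% | -4.1 | 60% | +10 |
| 30% | 43.9% | -6.1 | 65% | +15 |
| 50% | 39.9% | -10.1 | 75% | +25 |

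For other TEAEs over all assumed values, the smallest gap is -0.6 points (p = 30%, stop after 56 days, f = 10%) and the largest is -12.1 points (p = 70%, stop after 28 days, f = 50%). For any TEAE with stops counted, the gap runs from +3 to +35 points, and these are real events.

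**Step 4: what could be hidden.** At p = 50% and a stop after 28 days, I solved (1 - f)(1 - exp(-Hλ·114)) + f(1 - exp(-Hλ·58)) = 0.5 for the hazard ratio H. The result is 1.13, 1.20 and 1.38 for f = 20, 30 and 50%. A true increase of that size would show as equal crude percentages.

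**Step 5: study-wide termination alone.** Assume entry uniform over the 200 days before the cut-off, with exposure capped at 84 days. Mean exposure is 84 - 84²/400 = 66.4 days. The mean square is 84³/600 + 84² × 0.58 = 5080, so the SD is √(5080 - 66.36²) = 26.0 days. The expected difference between arms is 0, with chance SD 26.0 × √(1/20 + 1/10) = 10.1 days.

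**The case against.** A reader might go further and infer that the arm with more early stops will look safer overall. The documents do not support this. Protocol 11.1.5 requires an abnormality that leads to discontinuation to be recorded as an adverse event, or a serious one, where it meets the definition. A subject stopped for a liver finding would therefore normally already be in the any-TEAE count. SAP 6.3.1.8 also tabulates TEAEs leading to discontinuation, and SAP 6.3.2.8 tabulates liver enzyme and bilirubin elevations and possible Hy's Law cases. Step 3 shows the any-TEAE percentage rising in that case. It could fall only where stops are not themselves TEAEs.

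A reader might also infer that termination biases the comparison, or that liver stops fell mainly on GLPG3970. Termination halts both concurrently randomised arms at one calendar point, so it causes only chance imbalance. The stopping rules are the same in both blinded arms, and no stops by arm are reported.

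Further points carry weight. Safety is descriptive by design (SAP 6.3), and the SAP follows the protocol in using subject percentages. At 20 versus 10 subjects and a percentage near 50%, a 90% CI for a difference is about ±1.645 × √(0.25 × 0.15) = ±32 points, well beyond the shifts computed here. Exposure by arm is tabulated, so a large imbalance would be visible, unless that provision is among those greyed out, which the extracted text cannot show. That table gives dosing duration, however, not time at risk for a first event, so it cannot be combined with subject counts to give a rate.

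**Conclusion.** The point holds as a cheap improvement. The plan has no measure of TEAE frequency that allows for time at risk, although that time varies with dosing and the SAP was finalised after the termination recommendation. If early stops differ by arm, percentages for TEAEs other than the stopping event can be too low in the arm with more stops, by about 1 to 12 points. That range rests on the assumed TEAE rates, stopping shares and stopping times and on a constant, equal hazard. Later-onset events are the most exposed, because a shortened window cuts off its late part. Counts of any TEAE, of discontinuations and of hepatotoxicity are not understated when the stopping event is itself a TEAE. The chance imbalance from termination is modest, with an SD of about 10 days under the assumed entry pattern. At this sample size the change would make the tables easier to read correctly; it is unlikely to reverse a conclusion.

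**What to change.** In SAP 6.3.1.8, keep n (%) and add two lines per arm for each of these categories: any TEAE; IP-related; Grade 3 or higher; serious; and liver-related, defined as the MedDRA hepatobiliary disorders class plus liver-related investigations terms. The last needs its own definition because SAP 6.3.1.7 names no events of special interest.

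- Total subject-weeks at risk, from first dose to the earliest of first event in the category, last dose + 30 days, or last contact.
- Subjects with an event per 100 subject-weeks, with an exact Poisson 90% CI.

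Label the output descriptive, without testing. Amend SAP 4.4.1.3 to state this censoring, and align the while-on-treatment wording in SAP section 3 with the 30-day limit in SAP 6.3.1.1.

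The cost is one time-to-first-event derivation per category, from dates already collected, with a stated rule for incomplete start dates. The rate assumes a roughly constant hazard, which may fit liver events poorly, so the percentages should stay beside it. Intervals will be wide.

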#### **6.3.1.9. EudraCT Adverse Events Reporting**

For the purpose of EudraCT reporting, the following tabulations will be created:

Frequency tabulations, by system organ class and preferred term, of the number (percent) of subjects and number of events with non-serious TEAE will be presented. A similar table will be

provided for all serious TEAEs, as well as a table for non-serious TEAEs reported in at least two subjects in any treatment group.

### **6.3.2. Laboratory Safety**

#### **6.3.2.1. Available Data**

Laboratory tests scheduled are described in the protocol section 8.5.2. In addition, the derived laboratory tests described in Section [6.3.2.2](#) will be added.

The statistical analyses will only present results in Standard International (SI) standardized units. Other units will not be presented.

Only data provided by the central laboratory will be used in tables and figures. Results from local labs will be listed only.

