Appendix 15: Algorithm for Elevated Liver Function Tests

	AST or ALT increase to				
Value Range	>=1.5x to 3xULN	>=3x to <5xULN	>=5x to <8xULN	>=3xULN with signs of liver damage ¹	>=8xULN
IP Action	Continue as planned	Reduce or interrupt IP for at least 2 weeks	Interrupt IP for at least 2 weeks	Discontinue IP ²	Discontinue IP ²
		Close observation ²	Close observation ²		
After at least 2 weeks	AST and ALT <3xULN	AST or ALT >=3xULN			
	Weekly LFTs for the first 2 weeks (biweekly for the following weeks, or more frequently at investigator's discretion)	Discontinue IP Report SAE and complete liver event page for any of abnormalities listed below ³ : - AST/ALT increase >=3xULN with signs of liver damage ¹			

¹ Signs of liver damage:

- total bilirubin >=2.0xULN OR INR >1.5, and/or
- symptoms: appearance of fatigue, nausea, vomiting, right upper abdominal quadrant pain or tenderness, fever, rash and/or eosinophilia (>5%)

² Close observation recommendations:

- Monitor 2 to 3 times per week all of the following parameters: ALT, AST, alkaline phosphatase, total bilirubin, eosinophils, INR. If local regulations allow, home visits can be performed if subjects cannot come to the clinical study center.
- Frequency of retesting can be reduced to once a week or less if abnormalities stabilize or the IP has been discontinued; however, monitoring might still be needed more frequently taking into consideration the SoC and/or changes to this.
- Based upon investigator's discretion gastroenterology or hepatology consultations, additional serology testing, imaging, and pathology assessments may be required.
- Re-query history of symptoms, prior and concurrent diseases, concomitant medication and non-prescription medicines, herbal, dietary supplements, alcohol use, recreational drug use, special diets.

- Rule out all of the following: acute viral hepatitis, autoimmune hepatitis, alcoholic hepatitis, non-alcoholic fatty hepatitis, hypoxic/ischemic hepatitis, biliary tract disease, and cholestasis.

- Re-query exposure to environmental chemical agents.

³ The following steps should be followed:

- The site should immediately contact the subject and require the subject to discontinue IP immediately. The subject should be asked to return to the site within a 48-hour window from awareness of the result.
- A full evaluation of various causes of hepatitis should be conducted (i.e. infectious, alcohol, medications, anatomical).

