### 6.3.2.8. Hepatotoxicity

Hepatotoxicity will be investigated by tabulating the aspartate aminotransferase (AST) and alanine aminotransferase (ALT) values categorized as  $>3$ ,  $>5$ ,  $>10$  and  $>20$  times their upper limit of normal (per analyte and over both analytes combined), ALP categorized as  $> 1.5$  times the upper limit and total bilirubin as  $> 2$  times the upper limit of normal. Elevations of AT (AST or ALT)  $> 3$  times their upper limits accompanied by elevated total bilirubin ( $>1.5 \times \text{ULN}$ ,  $>2 \times \text{ULN}$ ) on the same day will also be tabulated.

To assess the potential of the drug to cause severe liver damage, possible Hy's Law cases will be identified. These subjects are defined as having any elevated AT (AST or ALT) of  $>3 \times \text{ULN}$ , ALP  $<2 \times \text{ULN}$ , and associated with an increase in total bilirubin  $>2 \times \text{ULN}$  on the same day.

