### 6.3.2.9. Presentation of Results

Continuous laboratory tests including, glucose, cholesterol, triglycerides, low-density lipoprotein (LDL), high-density lipoprotein (HDL) and fasted glucose, will be summarized by means of descriptive statistics (including 90% CI of the mean change) by laboratory test, treatment group and analysis window. Actual values and change from baseline will be tabulated separately.

Profile line plots by subject of all actual observed values using relative day (ADY) and profile plots on change from baseline by analysis window will be presented by treatment group. All values, including unscheduled visits will be presented in profile plot. If there are more than one visits on the same day, time will be considered to order them. Graphs of the mean (+ SE) actual values over time and the mean (+ SE) change from baseline, and percent changes from baseline will be presented for all continuous laboratory parameters, with the exception of the metabolic markers.

The analysis of abnormalities will focus on assessments reported during the treatment period. Results reported before baseline will only be listed.

Non-graded abnormalities and toxicities grades of the actual values will be presented as shift tables of the worst-case abnormality/toxicity grade versus the baseline abnormality/toxicity grade. The table will be created per laboratory test, treatment group and analysis window. The results of non-graded abnormalities and toxicities grades will be shown separately.

A frequency table of the number (percent) of subjects with treatment-emergent worst-case abnormalities/toxicity grade per laboratory test, treatment group and analysis period will be presented. The results of non-graded abnormalities and toxicities grades will be shown separately.

A frequency table of the number (percent) of subjects will be also provided for hepatotoxicity flags defined before. These abnormalities will be also flagged in the individual data laboratory listing.

Listing will be provided for the laboratory test along with flag for abnormality results. In addition, pregnancy result will be listed separately.

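### The central-laboratory-only rule has no exception for the hepatotoxicity and Hy's Law tables, so any liver follow-up value measured locally would be left out of them

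*SAP*

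**What the plan says.** SAP 6.3.2.1 sets the data source for the whole Laboratory Safety section: "Only data provided by the central laboratory will be used in tables and figures", and then "Results from local labs will be listed only".

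SAP 6.3.2.8 falls within that section. It states: "Hepatotoxicity will be investigated by tabulating the aspartate aminotransferase (AST) and alanine aminotransferase (ALT) values", by multiples of the ULN. It adds rows for ALP and total bilirubin, and a table of raised transaminase with raised bilirubin on the same day. It also says that "possible Hy's Law cases will be identified" from transaminase, ALP and bilirubin on the same day. SAP 6.3.2.9 makes the output a table: "A frequency table of the number (percent) of subjects will be also provided for hepatotoxicity flags defined before". It also flags these abnormalities in the individual laboratory listing. Neither subsection mentions local results.

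SAP section 1 records that the Safety Monitoring Committee recommended termination "due to a safety signal of liver toxicity" on 26 November 2021, and that only the primary endpoint and safety analyses remain. The SAP is dated 17 December 2021.

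Protocol 8.9 sends routine safety samples to a central laboratory and names only SARS-CoV-2 tests as possibly local. For raised transaminases, Protocol Appendix 15 asks sites to "Monitor 2 to 3 times per week all of the following parameters: ALT, AST, alkaline phosphatase, total bilirubin, eosinophils, INR", with home visits possible. Protocol 6.4 and Appendix 15 ask certain subjects to return within 48 hours, and 6.4 adds repeat liver tests. None of these places says which laboratory analyses the samples.

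**The concern.** Central-only data are a sensible default for means and changes from baseline, where mixing assays adds noise. The hepatotoxicity outputs have a different purpose, which the SAP gives as "To assess the potential of the drug to cause severe liver damage". They depend on single extreme values and on same-day combinations, so one omitted result can remove a subject from a row. The extra liver samples are also the ones whose laboratory the protocol leaves unstated.

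The table in question measures the signal that ended the trial, and it will appear in an abbreviated report limited to the primary endpoint and safety. If local liver results exist and are excluded, the report could understate how high values rose or how many subjects met the combined criteria.

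**Working it through.** No planned figure depends on this rule, so there is none to reproduce. The check is on the text, followed by arithmetic for scale.

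**1. Does the rule reach the liver outputs?** Yes. Section 6.3.2.1 covers all laboratory tables and figures, the outputs of 6.3.2.8 are laboratory tables, and no exception is written in 6.3.2.8 or 6.3.2.9.

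**2. Does it sit well with the rest of the SAP?** Not fully. For worst-case toxicity grades, 6.3.2.7 uses all non-missing post-baseline records, including unscheduled and follow-up visits, so that peaks are captured. Under 6.3.2.1 this can mean central records only.

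**3. Could local liver values arise?** The documents leave this open. Routine safety samples are central (Protocol 8.9). Follow-up liver tests have no laboratory assigned.

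**4. How many samples could be involved?** Visits after Day 8 are on Days 29, 57 and 85 (SAP 2.3), so the gaps are 29 − 8 = 21, 57 − 29 = 28 and 85 − 57 = 28 days. If monitoring 2 to 3 times per week ran through a whole gap:

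- 21 days: 3 weeks × 2 to 3 = 6 to 9 samples
- 28 days: 4 weeks × 2 to 3 = 8 to 12 samples

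These are upper illustrations, because Appendix 15 lets the frequency fall once values stabilise or treatment has stopped.

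**5. What would be lost if some were local?**

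| Situation | Effect on the SAP 6.3.2.8 tables |
|---|---|
| Only qualifying value is local | Subject missing from the row |
| Triggering transaminase central, later peak local | Normally still in the >3 × ULN row; may be missing from >5, >10 or >20 × ULN |
| Transaminase central, that day's bilirubin local | Missing from the combined table and from Hy's Law identification |
| Transaminase and bilirubin central, that day's ALP local | ALP condition (<2 × ULN) for Hy's Law cannot be confirmed |

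**6. Size per subject.** Planned arms are 20 and 10 (SAP 2.6); the numbers treated at termination are not given. One subject is 1/20 = 5.0 percentage points on GLPG3970 and 1/10 = 10.0 points on placebo. Exact (Clopper-Pearson) 90% limits are the 0.05 quantile of Beta(x, n − x + 1) and the 0.95 quantile of Beta(x + 1, n − x). The SAP does not plan intervals for these flags; they are shown only to indicate precision.

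| Arm | One case counted | Same case not counted |
|---|---|---|
| GLPG3970, n = 20 | 5.0% (0.3 to 21.6) | 0% (0 to 13.9) |
| Placebo, n = 10 | 10.0% (0.5 to 39.4) | 0% (0 to 25.9) |

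**7. Can a local value be used?** Yes. The categories in 6.3.2.8 are all multiples of the ULN, so a local result divided by that laboratory's own ULN can be classified without conversion.

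**The case against.** The strongest reply is that the premise is not documented. Routine safety samples are central, SARS-CoV-2 tests are the only local testing the protocol names, and the sentence on local results may be generic or written with those tests in mind. Home visits concern where blood is drawn, not where it is analysed. Unscheduled samples sent to the central laboratory already count. This stands: the gap is conditional.

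A second reply is that a local peak is not invisible. It stays in the listings. Under Protocol 11.1.5, AST or ALT at or above 3 × ULN with signs of liver damage must be reported as a serious adverse event, whichever laboratory measured it. SAP 6.3.1.8 tabulates serious events, grade 3 to 5 events and events leading to interruption or discontinuation of treatment. With about 30 planned subjects, a listing can be read case by case. This stands in part. Event tables show terms and grades, not ULN multiples or Hy's Law status. Listings give no rate by arm, and 6.3.2.9 does not say whether its flags cover local values.

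A reader might infer more than the documents support:

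- **That the worst values were probably local.** Nothing shows that any liver test was run locally.
- **That the loss falls mainly on the active arm.** The rule is the same in both arms, and on planned sizes a missed placebo case moves its rate more.
- **That every missed local value costs 5 points.** That needs a GLPG3970 subject whose only qualifying value is local. Close observation starts at 3 × ULN, so a subject whose triggering value was central already meets, or sits at the edge of, the >3 × ULN row.
- **That local values vanish from every table.** The rule covers laboratory tables and figures, not adverse event tables.

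**Conclusion.** The point holds as a conditional gap. As written, the SAP keeps any local liver result out of the hepatotoxicity categories, the same-day transaminase/bilirubin table and Hy's Law identification. The protocol does not rule such results out for liver follow-up.

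If they exist, the tables can undercount the signal that stopped the trial: by 5 points per GLPG3970 subject or 10 per placebo subject when the only qualifying value is local, and otherwise mainly in the higher multiples and the bilirubin pairing. These steps assume the planned arms of 20 and 10. If no local liver values exist, nothing is lost. The documents do not establish that the signal was understated, or in which arm.

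**What to change.** In SAP 6.3.2.1 and 6.3.2.8:

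- Keep central-only data for continuous summaries.
- Include any local AST, ALT, ALP and total bilirubin, each as a multiple of the local laboratory's ULN and flagged by source, in the hepatotoxicity categories, the same-day transaminase/bilirubin table and Hy's Law identification.
- Alternatively, leave the main table central-only and place beside it a parallel table that includes the local values. This avoids mixing sources in the main output.

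The programming is minor. The main cost is obtaining local reference ranges: the documents do not show that these were collected, and because the SAP followed termination, collection may have to be retrospective. Some between-laboratory variation enters; the source flag lets a reader see which counts depend on it.
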